### 6.7.1. Extent of Exposure

The following exposure-related variables will be reported:

- **Cumulative dose (mg/kg)** is calculated as sum of all calculated dose levels, where calculated dose level (mg/kg) = (actual total dose [mg]) / (closest body weight [kg] prior to the treatment).
- **Duration of treatment (week)** is calculated as (date of last dose in last cycle – date of first dose + 14)/7.
- **Dose intensity (mg/kg/week)** is calculated as cumulative dose / duration of treatment.
- **Relative dose intensity (%)** is calculated as dose intensity / planned dose intensity \* 100.

The following analyses on the defined reexposure-related variables will be performed using summary statistics (number of patients, mean, and standard deviation) by dose group:

- Exposure: duration of treatment, number of cycles received, number of patients who received  $\geq 1$  cycle,  $\geq 2$  cycles, ...,  $\geq 8$  cycles; and cumulative dose.
- Dose adjustment: number of patients with dose adjustments: dose reduction, dose omission and dose delay; reason for dose adjustments.

- Dose intensity: weekly dose intensity, relative dose intensity.

### 6.7.2. Adverse Events

**Adverse events** are defined as any untoward medical occurrence in a patient administered a pharmaceutical product, without regard to the possibility of a causal relationship.

**Treatment-emergent adverse events (TEAE)** is defined as any untoward medical occurrence that either occurs or worsens at any time after treatment baseline and that does not necessarily have to have a causal relationship with this treatment.

**Serious adverse events (SAE)** are defined as any of the AEs that results in one of the following outcomes:

- death
- initial or prolonged inpatient hospitalization
- a life-threatening experience (that is, immediate risk of dying)
- persistent or significant disability/incapacity
- congenital anomaly/birth defect considered significant by the investigator
- considered significant by the investigator for any other reason based upon appropriate medical judgement

A summary overview of all AEs will be provided per study arm. The overview will tabulate number of subjects with:

- at least 1 TEAE
- at least 1 CTCAE grade  $\geq 3$  TEAE
- at least 1 serious AE
- discontinuation from study treatment due to AE
- discontinuation from study treatment due to SAE
- death due to AE on study treatment
- death due to AE within 30 days of last infusion or discontinuation from study treatment

The summary will be provided regardless of study drug causality, and repeated for events deemed by investigator to be possibly related to study medication.

The following summaries of TEAEs by treatment dose levels will be provided (\*repeated for events deemed by the investigator to be possibly related to study medication)

- by PT \*
- by maximum CTCAE grade and by SOC and PT

Consolidated AE may be summarized for TEAE and study treatment-related TEAE. A patient listing of all AEs will be provided.

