Defining RP2D: After accrual to dose level 2 is completed, PK comparisons from dose levels 1 and 2 will be performed. An expansion cohort will accrue at the lowest tolerable dose at which C_{min} of $\geq 50 \mu\text{g/mL}$ has been achieved in at least 5 out of 6 evaluable patients to acquire PK data in a representative number of young patients (i.e. patients < 12 years old). If at least 10 out of the total 12 evaluable patients have a steady state concentration of ramucirumab greater than $50 \mu\text{g/mL}$, then the RP2D has been defined. If $C_{min,ss}$ of $\geq 50 \mu\text{g/mL}$ has not been achieved in at least 5 out of 6 evaluable patients from dose level 2, and if the MTD has not yet been reached, then dose level 3 will be considered.

Update: The RP2D was determined to be 12 mg/kg.

5.3.2 **Part B:** Once the RP2D has been determined in Part A, Part B will open to enroll children with relapsed or refractory CNS tumors who will receive ramucirumab at the MTD or RP2D. Part B of the study will require up to 6 evaluable patients enrolled at the MTD or RP2D as determined in Part A (See [Section 11.1](#)).

5.3.3 **Intra-Patient Escalation**

Intra-patient dose escalation is not allowed.

5.4 **Grading of Adverse Events**

Adverse events (toxicities) will be graded according to the NCI Common Terminology Criteria for Adverse Events (CTCAE) version 5.0. All appropriate treatment areas should have access to a copy of the CTCAE version 5.0. A copy of the CTCAE version 5.0 can be downloaded from the CTEP web site http://ctep.cancer.gov/protocolDevelopment/electronic_applications/ctc.htm. Any suspected or confirmed dose-limiting toxicity should be reported immediately (within 24 hours) to the Study Chair.

5.5 **Definition of Dose-Limiting Toxicity (DLT)**

DLT will be defined as any of the following events that are possibly, probably or definitely attributable to protocol therapy. The DLT observation period for the purposes

THIS PROTOCOL IS FOR RESEARCH PURPOSES ONLY, SEE PAGE 1 FOR USAGE POLICY

of dose-escalation will be the first cycle of therapy.

Dose limiting hematological and non-hematological toxicities are defined differently.

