11.6 Statistical methods

11.6.1 **Analysis Sets**

Safety Analysis Set (SAS) will consist of subjects who receive any amount of study drug.

11.6.2 **Dose Evaluable Set (DES)** will consist of: 1) subjects who receive any amount of study drug and then experience DLT during Cycle 1; and 2) subjects who receive at least 85% of the prescribed dose in Cycle 1 and have an adverse event assessment in the first cycle. DES will be used for evaluation of each dose level for dose-escalation.

11.6.3 **Pharmacokinetic Analysis Set (PAS)** will include subjects who have sufficient PK data to derive at least one PK parameter.

11.6.4 **Efficacy Analyses:**

Preliminary efficacy analyses will also be performed by dose cohort for the Safety Analysis Set. Data cut-off for primary study analysis will occur when all enrolled subjects have completed 6 cycles of treatment or discontinued study drug administration. After the final analysis, additional analyses may be performed as appropriate.

11.6.5 **Pharmacokinetic Analyses**

Serum concentrations of Ramucirumab will be tabulated and summarized by dose level and time. Ramucirumab PK parameters will be derived from serum concentrations by non-compartmental analyses using actual times. Minimally, the following PK parameters will be calculated: C_{max} , t_{max} , and $AUC (t_{1/2}, CL, and Vd_{ss})$ will be calculated only if the data permit). Additional analysis utilizing the population pharmacokinetic approach may also be conducted if deemed appropriate.

11.6.6 **Immunogenicity Analyses**

Immunogenicity incidence will be tabulated, and correlation of immunogenicity to ramucirumab drug level, activity, and safety will be assessed as appropriate.

11.6.7 **Statistical Analyses**

Baseline demographics and baseline disease characteristics will be summarized for all enrolled patients who had at least one dose of study therapy.

Listing of patients including those treated at the MTD will be generated.

Treatment-emergent CTCAEs will be summarized by each dose level and for

THIS PROTOCOL IS FOR RESEARCH PURPOSES ONLY, SEE PAGE 1 FOR USAGE POLICY

overall population by each CTCAE grade separately.

Best overall response, duration of response, and duration of stable disease will also be summarized descriptively by each dose level.

Listing of deaths on study or 30 day post-discontinuation will be provided. Listing of SAEs will also be produced. Listing of AEs leading to treatment discontinuation will be provided.

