## 4. Study Objectives

### 4.1. Primary Objective

The primary objectives of the study are as follows:

- to estimate the maximum tolerated dose (MTD) and/or recommended Phase 2 dose (RP2D) of ramucirumab administered as an intravenous (IV) infusion over 60 minutes, every 2 weeks, to children with recurrent or refractory solid tumors
- to determine the tolerability of the MTD and/or RP2D of ramucirumab in children with recurrent or refractory central nervous system (CNS) tumors
- to define and describe the toxicities of ramucirumab administered on this schedule
- to characterize the pharmacokinetics (PK) and immunogenicity of ramucirumab in children with recurrent or refractory solid tumors including CNS tumors

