## 5. Study Design

### 5.1. Summary of Study Design

The study will be completed in 2 parts. Part A will be a safety and dose-finding phase of the study for patients with non-CNS solid tumors, and will include dose-escalation and dose-expansion components. Part B will include a safety evaluation specifically for patients with CNS tumors.

For the dose-escalation phase, a rolling 6 design will be used. Starting dose will be 8 mg/kg IV every 2 weeks (Q2W) with 3 doses per 42 day cycle (Dose Level 1). The decision rules of dose level assignment based on dose-limiting toxicity (DLT) are introduced in the section below. If the MTD is not exceeded (0 or 1 DLT/6 fully evaluable patients) at 8 mg/kg dose level, a second dose level will be explored at the escalated dose of 12 mg/kg IV Q2W with 3 doses per cycle (Dose Level 2). After accrual to Dose Level 2 is completed, PK comparisons from dose levels 1 and 2 will be performed. The goal is to expand at the dose level at which at least 5 out of 6 patients achieve a day 42  $C_{min} \geq 50 \mu\text{g/mL}$ . If PK analysis indicates that more than 1 patient treated at 12 mg/kg dose level has a day 42  $C_{min}$  significantly less than 50  $\mu\text{g/mL}$ , and the MTD has not been exceeded, additional dose levels will be considered. If the MTD in children and adolescents is exceeded at 8 mg/kg IV Q2W, de-escalation to 6 mg/kg will be considered, and the recommended dose will be based on the MTD.

An expansion cohort will accrue at the lowest tolerable dose at which  $C_{min}$  of  $\geq 50 \mu\text{g/mL}$  has been achieved in at least 5 out of 6 evaluable patients, to acquire PK data in a representative number of young patients (ie, patients <12 years old). If at least 10 out of the total of 12 evaluable patients have a steady state concentration of ramucirumab greater than 50  $\mu\text{g/mL}$ , then the RP2D has been defined.

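### No planned summary is by Part, so the dose-level safety, exposure and PK tables would merge Part B (CNS) with the Part A 12 mg/kg cohort, and CNS tolerability has no summary table of its own

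*SAP*

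**What the plan says.** The CNS question stands alone among the primary objectives. SAP 4.1, matching Protocol 1.1.2, sets out "to determine the tolerability of the MTD and/or RP2D of ramucirumab in children with recurrent or refractory central nervous system (CNS) tumors". SAP 5.1 describes the design accordingly: "Part B will include a safety evaluation specifically for patients with CNS tumors".

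The dose is shared. Protocol 5.3.2 says that "Part B will open to enroll children with relapsed or refractory CNS tumors who will receive ramucirumab at the MTD or RP2D", and the update in Protocol 5.3.1 records the result: "The RP2D was determined to be 12 mg/kg".

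The planned outputs name these stratifiers:

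- TEAE tables: "The following summaries of TEAEs by treatment dose levels will be provided" (SAP 6.7.2). Protocol 11.6.7 also uses dose level and adds the overall population.
- Exposure, dose adjustment and dose intensity: "will be performed using summary statistics (number of patients, mean, and standard deviation) by dose group" (SAP 6.7.1).
- PK: "Serum concentrations of Ramucirumab will be tabulated and summarized by dose level and time" (Protocol 11.6.5). SAP 6.6 names no stratifier.
- AE overview: by *study arm* (SAP 6.7.2), a term that neither document defines.
- SAE, AESI, death and laboratory-shift summaries: no stratifier named (SAP 6.7.3 and 6.7.4).
- DLTs: listed for *Phase 1a* only, by dose schedule (SAP 6.7). *Phase 1a* is not defined either.

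No analysis paragraph in either document names Part, or CNS versus non-CNS, as a stratifier.

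**The concern.** The design keeps CNS patients apart for a reason. Part A excludes CNS metastases (Protocol 4.1.2). Part B has its own exclusion for hemorrhage on the baseline MRI (Protocol 4.2.4) and requires gradient MRI sequences to look for hemorrhage (Protocol 8.1, tumor evaluation footnote). The main tables, however, separate patients only by dose, and at 12 mg/kg dose no longer identifies the Part.

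A programmer who follows the text would produce one 12 mg/kg column holding both populations. An excess of events, dose holds or dose reductions in CNS patients would be averaged with the larger Part A group, and the reader would have no summary rate for the population that objective 1.1.2 names. The DLT output has a further gap: if *Phase 1a* means Part A, Part B DLTs are not listed at all.

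**Working it through.** **Inputs**

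- Part A evaluable patients at the RP2D: 12, counting escalation and expansion. SAP 5.1: "If at least 10 out of the total of 12 evaluable patients have a steady state concentration of ramucirumab greater than 50" µg/mL.
- Part B evaluable patients: up to 6, or 12 if two different classes of DLT lead to expansion (Protocol 11.1).
- Tolerability limit: a dose is within the MTD if fewer than one-third of patients have a DLT (Protocol 11.2.2).

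**Step 1. The plan's own figures.** Part B enrolment is 6 / (1 − 0.20) = 7.5, rounded up to 8, as stated. Expanded, it is 12 / 0.80 = 15, as stated. For Part A, 24 × 1.20 = 28.8 gives the stated 29 (24 / 0.80 would give 30). That one-patient difference has no bearing here.

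**Step 2. Who shares the column.** At 12 mg/kg there are 12 + 6 = 18 evaluable patients, of whom 6/18 = 33% are CNS patients. If Part B is expanded, there are 12 + 12 = 24, of whom 12/24 = 50% are CNS patients.

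**Step 3. When a merged column hides Part B.** DLTs are used because the protocol gives a limit for them; the same arithmetic applies to any event. Let a be the number of Part A patients with a DLT out of 12, and b the number in Part B out of 6. Part B is at or above the limit when b ≥ 2. The merged rate is below it when (a + b)/18 < 1/3, that is a + b ≤ 5. Both hold in these cases:

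| Part B | Part A | Merged |
|---|---|---|
| 2/6 (33%) | 0 to 3 of 12 | 2/18 to 5/18 (11% to 28%) |
| 3/6 (50%) | 0 to 2 of 12 | 3/18 to 5/18 (17% to 28%) |
| 4/6 (67%) | 0 or 1 of 12 | 4/18 to 5/18 (22% to 28%) |
| 5/6 (83%) | 0 of 12 | 5/18 (28%) |

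For the expanded Part B, 4/12 (33%) with 0 to 3 of 12 in Part A merges to 4/24 to 7/24 (17% to 29%).

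**Step 4. How often, under assumed rates.** The documents give no true DLT rates. Assume 5% to 20% in Part A and 33% to 50% in Part B. The probability that b ≥ 2 while a + b ≤ 5 is the sum of Binomial(12, pA) × Binomial(6, pB) over those pairs. It runs from 0.405 (pA = 20%, pB = 33%) to 0.798 (pA = 5%, pB = 50%).

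**Step 5. What a separate column offers.** For 2/6 the exact 95% interval is 4% to 78%. A Part B column is imprecise, but it describes the population named in the objective.

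**The case against.** The strongest case on the other side is that the plan never says the Parts will be combined. SAP 5.1 states the opposite intent for Part B; *study arm* and *dose group* could be programmed as Part by dose; all these analyses are descriptive (Protocol 11.5); and SAP 6 allows analyses that it does not specify. This stands as far as it goes: merging is the literal reading and not an announced decision. But a primary objective should not depend on how a programmer resolves an undefined term when the stated rule for the TEAE tables is dose.

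A reader might infer more than the documents support:

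- *That every summary is by dose level.* The AE overview is by *study arm*, and the SAE, AESI, death and laboratory-shift summaries name no stratifier. None of these is by Part either.
- *That CNS tolerability cannot be seen at all.* Part B is a separately counted cohort with its own DLT-driven expansion (Protocol 11.1). The study chair's DLT evaluations are reviewed weekly (Protocol 14.4.2). Listings of AEs, SAEs, AESIs, and AEs leading to death, discontinuation or dose modification are planned (SAP 6.7.2 and 6.7.3). With 6 to 8 patients, a serious CNS event would be visible there. Listings are still no summary of a primary objective.
- *That the PK objective fails.* Objective 1.1.4 covers solid tumors including CNS tumors as one population and does not ask for a separate CNS result.
- *That merging undermines the RP2D.* The RP2D was fixed in Part A before Part B opened (Protocol 5.1 and 5.3), so only descriptive reporting is affected.

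**Conclusion.** The point holds for the summary tables. Objective 1.1.2 has no summary table of its own, and the TEAE, exposure, dose-adjustment and serum concentration outputs, followed literally, place about 6 CNS patients (12 if Part B is expanded) in one 12 mg/kg column with about 12 Part A patients. Part B could sit at the one-third DLT limit with 2/6 while the merged rate reads 11% to 28%. DLT reporting for Part B is unclear until *Phase 1a* is defined.

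The sizes rest on planned evaluable numbers. The safety population is everyone who received any drug (SAP 6), so actual counts will differ, with up to 8 enrolled in Part B, or 15 if it is expanded. The event counts illustrate what could occur and do not predict it. The probabilities in Step 4 depend wholly on the assumed rates. Dose decisions are not affected. The change should be made because it concerns a primary objective and costs almost nothing.

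**What to change.** 1. In SAP 6.7.1 and 6.7.2 and Protocol 11.6.5 and 11.6.7, replace dose level or dose group as the sole stratifier with these columns: Part A by dose level, Part B, pooled 12 mg/kg, and total.
2. Use the same columns in place of *study arm* in the AE overview (SAP 6.7.2).
3. State the same columns for the SAE, AESI, death and laboratory-shift summaries (SAP 6.7.3 and 6.7.4), which now name none.
4. In SAP 6.7, replace the *Phase 1a* restriction with a DLT summary for each Part in DLT-evaluable patients. An exact interval for Part B would show how little 6 patients can say.

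Part membership follows from diagnosis at enrollment (Protocol 4.1.2), so the cost is SAP and protocol wording plus extra table columns, with no new data, no additional patients and no change in sample size.

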### **6.7.3. Deaths, Other Serious Adverse Events, and Other Notable Adverse Events**

Reasons for deaths will be summarized separately for 1) all deaths, 2) deaths on therapy, 3) deaths within 30 days of treatment discontinuation, and 4) deaths after 30 days of treatment discontinuation.

Serious AEs will be summarized by PT, and repeated for serious adverse events deemed by the investigator to be possibly related to study medication, with consolidated summary performed if needed. A listing of SAEs will be produced.

In addition, the following analyses will be performed:

- adverse events leading to death by PT
- adverse events leading to study treatment discontinuation by PT
- adverse events leading to study treatment dose modification by PT
- adverse events of special interest (AESI) by PT, and repeated for AESIs deemed by the investigator to be possibly related to study medication
- listings of AESI, AEs leading to death, AEs leading to discontinuation, and AEs leading to dose modifications

### **6.7.4. Clinical Laboratory Evaluation**

The severity of laboratory results will be classified according to CTCAE version 4.0. The shifts in CTCAE toxicity grading from baseline to worst grade postbaseline (first dose up to 30 days after study treatment discontinuation) will be produced.

A patient listing of all laboratory will be provided with a flag for values outside of the laboratory normal range as well as investigator site, patient identifier, age, gender, race, weight, and visit.

### **6.7.5. Vital Signs and Other Physical Findings**

All vital signs including temperature, blood pressure, heart rate, and respiratory rate will be listed for all enrolled patients.

## **6.8. Annual Report Analyses**

The following reports are needed for a Development Update Safety Report (DSUR):

- estimated cumulative subject exposure
- cumulative exposure to investigational drug, by demographic characteristics for ongoing unblinded clinical trials and completed clinical trials
- exposure information for ongoing clinical trials and clinical trials that completed during the reporting period
- listing of subjects who died during the DSUR reporting period
- discontinuations due to AEs during the DSUR reporting period

## 6.9. Clinical Trial Registry Analyses

Additional analyses will be performed for the purpose of fulfilling the Clinical Trial Registry (CTR) requirements.

Analyses provided for the CTR requirements include the following:

Summary of adverse events, provided as a dataset which will be converted to an XML file. Both Serious Adverse Events and ‘Other’ Adverse Events are summarized by treatment group and by Medical Dictionary for Regulatory Activities (MedDRA) PT.

- An AE is considered ‘Serious’ whether or not it is a TEAE.
- An AE is considered in the ‘Other’ category if it is both a TEAE and is not serious. For each Serious AE and ‘Other’ AE, for each term and treatment group, the following are provided:
  - the number of participants at risk of an event
  - the number of participants who experienced each event term
  - the number of events experienced
- Consistent with [www.ClinicalTrials.gov](http://www.ClinicalTrials.gov) requirements, ‘Other’ AEs that occur in fewer than 5% of patients/subjects in every treatment group may be excluded if a 5% threshold is chosen.
- adverse event reporting is consistent with other document disclosures for example, the clinical study report (CSR), manuscripts, and so forth.

